Maximizing Visual Outcomes with Eyhance IOLs

NCT05611073

25 Jan 2022

PROTOCOL TITLE: Maximizing Visual Outcomes with Eyhance IOLs

STUDY TREATMENTS: None

Study Objectives:

The objective of this study is to demonstrate which pre-operative biometric findings or measurements could indicate increased intermediate or near vision in a patient receiving an Eyhance IOL.

The objective will be completed by measuring visual outcomes at distance, intermediate, and near when corrected to plano sphere as well as obtaining or reviewing biometric measurements in a controlled setting. In addition, the patients will also fill out a questionnaire to determine their level of spectacle independence and satisfaction.

Clinical Hypothesis:

Eyhance IOLs provide intermediate vision based on benchmark defocus curves. Some Eyhance patients also appear to have vastly improved intermediate and even near vision compared to other patients who have received an Eyhance IOL. This study aims to determine which biometric properties (such as spherical aberration, q value, pupil size, etc) can be targeted for these outcomes. Patients will be assessed for corrected monocular and binocular distance, intermediate, and near vision at plano. Lastly patient satisfaction score between the two groups will also be determined.

OVERALL STUDY DESIGN

This is a non-interventional prospective, single center, bilateral, non-randomized, open-label, observational clinical study. All patients will have had bilateral implantation of an Eyhance IOL at the time of cataract surgery. These patients will then be assessed in the 1–6-month post-operative period. Patients will be grouped into two arms: “distance with minimal intermediate” and “distance with enhanced intermediate/near” based on mean photopic binocular BCDVA and DCIVA (at 66 cm) of patients with bilateral Eyhance IOLs corrected to plano sphere. The “distance with minimal intermediate” group is defined by BCDVA of 0.1 logMAR or better but a DCIVA of 0.4 logMAR or worse. The “distance with enhanced intermediate/near” is defined by BCDVA of 0.1 logMAR or better and a DCIVA of 0.3 logMAR or better. In addition to binocular BCDVA and DCIVA, monocular measurements will be obtained as well. The two groups will be compared to assess which patient biometric properties (such as spherical aberration, q value, pupil size, etc) lead to an overall increase in near or intermediate vision as well as overall patient satisfaction. Biometric data will be obtained from the Zeiss IOL Master 700, Atlas 9000, and the iDesign.

Duration:

3 months or longer to meet required enrollment.

Administration:

Patients with previously implanted bilateral Eyhance IOLs will be offered the opportunity to participate in the study.

Visit Schedule:

All subjects will undergo 1 visit. At the study visit and after informed consent, the subjects' demographic information will be collected, and the subject will have the following testing:

- 1) Manifest refraction
- 2) Best corrected distance visual acuity
- 3) Distance corrected intermediate visual acuity
- 4) Distance corrected near visually acuity
- 5) Binocular best corrected distance visual acuity
- 6) Binocular distance corrected intermediate visual acuity
- 7) Binocular distance corrected near visually acuity
- 8) Pupil measurements (photopic and/or mesopic – automated and manual)
- 9) Review or remeasurement of biometry (IOL Master 700 or Atlas 9000 topography)
- 10) iDesign measurement

STUDY POPULATION CHARACTERISTICS:

Condition

Patients with healthy eyes and bilateral implantation of Eyhance IOLs.

Number of Subjects:

Per Green, for multiple variables in a regression analysis, $N = 50 + 8(m)$ per arm should be sufficient for appropriate power, assuming a beta of 0.2 and an alpha of 0.05 for a power of 80%. Assuming 6 variables (pupil size, q value, spherical aberration, AC depth, axial length, average K power), approximately 110 patients (220 eyes) will be required.

Source: Green, Samuel B. "How Many Subjects Does It Take To Do A Regression Analysis." *Multivariate behavioral research* 26 3 (1991): 499-510 .

Inclusion/Exclusion Criteria (all study criteria apply to each study eye unless otherwise indicated):

Inclusions

- 1) Adults, 40 years of age having already undergone uncomplicated cataract removal by phacoemulsification with a clear corneal incision in both eyes.
- 2) Implantation of bilateral Eyhance IOLs (DIB00/DIU***).

- 3) Able to comprehend and willing to sign informed consent and complete all required testing procedures
- 4) Best Corrected Distance Visual Acuity (BCDVA) projected to be 0.10 logMAR (Minimum Angle of Resolution) or better
- 5) Clear intraocular media
- 6) Minimum of two weeks post YAG capsulotomy to treat PCO

Exclusions

Subjects will not be permitted to enroll in this study if they meet any of the following exclusion criteria:

- 1) Any corneal abnormality, other than regular corneal astigmatism (as determined by pre-operative testing) that in the opinion of the investigator would confound the outcome(s) of the study
- 2) Any complication during cataract surgery (capsular tear, vitrectomy, etc)
- 3) History of or current retinal conditions or predisposition to retinal conditions
- 4) Amblyopia or strabismus in either eye
- 5) History of or current anterior or posterior segment inflammation of any etiology
- 6) Any form of neovascularization on or within the eye
- 7) Glaucoma (uncontrolled or controlled with medication)
- 8) Optic nerve atrophy
- 9) Subjects with diagnosed degenerative eye disorders
- 10) Postoperative CDVA worse than 0.10 logMAR (20/25 snellen).
- 11) Subjects who have an acute or chronic disease or illness that would confound the results of this investigation in the opinion of the investigator (e.g. immunocompromised, connective tissue disease, clinically significant atopic disease, etc)

EVALUATION CRITERIA:

The main objective of this study is to demonstrate which biometric characteristics can lead to enhanced intermediate or near vision in patients with prior bilateral Eyhance implantation.

Primary Clinical Endpoints:

- 1) To compare two groups categorized by “distance with minimal intermediate” and “distance with enhanced intermediate/near” based on mean photopic binocular BCDVA and DCIVA (66 cm) of patients with bilateral Eyhance IOLs targeted corrected at plano sphere.
- 2) To determine if any statistically significant differences in biometric data exists between the two groups including pupil size, spherical aberration, q value, etc. that may allow for pre-operative recognition of those patients who could have enhanced benefits of the Eyhance IOL. This will require multiple regression analysis given the large number of variables.
- 3) Comparison of a patient satisfaction survey between the two groups to assess for subjective differences in everyday life to determine if the enhanced vision plays a statistically significant difference in patients’ perceived quality of vision or quality of life.

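### Time since surgery varies from 1 to 6 months but enters no comparison; it could confound the satisfaction endpoint if acuity and satisfaction both drift over that period

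*Combined protocol and SAP*

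**What the plan says.** **Timing.** Overall Study Design states: "These patients will then be assessed in the 1–6-month post-operative period". Visit Schedule adds: "All subjects will undergo 1 visit". The study is described as observational and non-randomised.

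**Recruitment and eligibility.** Administration says: "Patients with previously implanted bilateral Eyhance IOLs will be offered the opportunity to participate in the study". Inclusion item 1 requires patients "having already undergone uncomplicated cataract removal by phacoemulsification with a clear corneal incision in both eyes". Neither gives a time limit. The only timing rule in the eligibility list concerns a different procedure: "Minimum of two weeks post YAG capsulotomy to treat PCO". No section says which eye's surgery starts the 1–6-month window, although the groups are defined by binocular acuity.

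**Analysis.** Number of Subjects lists the regression variables: "Assuming 6 variables (pupil size, q value, spherical aberration, AC depth, axial length, average K power), approximately 110 patients (220 eyes) will be required". Endpoint 2 says of the biometric comparison: "This will require multiple regression analysis given the large number of variables". Endpoint 3 is: "Comparison of a patient satisfaction survey between the two groups to assess for subjective differences in everyday life". Time since surgery is not among the six variables, the endpoints or the listed visit data, and no adjustment covariate is named for any comparison.

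**Source of the biometry.** Visit Schedule has pupil size and iDesign measured at the visit. IOL Master or Atlas values may be either looked up or measured again.

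**The concern.** Endpoint 3 aims to attribute a difference in perceived quality of vision or life to better intermediate and near acuity. Group membership depends on DCIVA at the single visit, and with only one visit the survey is presumably completed then too. If patients seen later tend to have both better DCIVA and higher satisfaction simply because more time has passed, the better-acuity group will contain more late visits. It will then look more satisfied even if acuity itself makes no difference. Opposing drifts could hide a real difference in the same way. The planned comparison has no means of separating the two explanations.

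For endpoint 2, pupil size is one of the six predictors and is measured at the visit, so it could in principle vary with the same clock.

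**Working it through.** **The plan's own figure.** The plan gives no number for timing. Its one computed figure is the sample size, which matters here only for the cost of an added covariate. The rule 50 + 8m with m = 6 gives 50 + 48 = 98 as a total, or 2 × 98 = 196 if applied per arm. Neither equals the stated 110. That is a separate matter from this point.

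**Inputs.** From the documents: a window of 1 to 6 months, one visit, alpha 0.05 (taken as two-sided) and about 110 patients. Assumed, because the documents are silent: visits spread evenly over the window; 55 patients per group; linear drift in DCIVA and satisfaction of 0.1 to 0.2 SD per month; and no link between the two except through time.

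**Step 1, spread of visit times.** SD = (6 − 1)/√12 = 1.443 months, so the variance is 2.083.

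**Step 2, loss of precision.** The share of outcome variance due to time is (drift × 1.443)².
- 0.1 SD per month: 0.1443² = 0.021, or 2%.
- 0.2 SD per month: 0.2886² = 0.083, or 8%.

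These correspond to correlations of about 0.14 and 0.29. An effect detectable with 80% power without this noise would have 79.7% power at r = 0.1, 78.5% at r = 0.2 and 76.3% at r = 0.3. The loss is small.

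**Step 3, gap in mean visit time between groups.** Chance alone gives a gap with standard error 1.443 × √(2/55) = 0.275 months. A systematic gap arises only if DCIVA itself drifts. Its approximate size is drift × 2.083 × k, where k is the distance between the group means of DCIVA in SD units.
- Split at the median, k = 2 × 0.798 = 1.596. Drift 0.1 gives 0.33 months; drift 0.2 gives 0.67 (0.68 by simulation).
- Patients with DCIVA between 0.3 and 0.4 logMAR belong to neither group. If they are the middle 20% (assumption), k = 2 × 0.386/0.4 = 1.93. Drift 0.1 gives 0.40 months. Drift 0.2 gives 0.78 or 0.82 by simulation, depending on whether the SD is taken within a time point or overall.

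**Step 4, spurious satisfaction difference and false-positive rate.** Spurious difference = satisfaction drift × gap. The rejection rate comes from a noncentral t with 108 degrees of freedom and noncentrality difference × √(55/2).

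| Drift in both (SD/month) | Gap (months) | Spurious difference (SD) | False-positive rate |
|---|---|---|---|
| 0.05, median split | 0.17 | 0.05 × 0.17 = 0.008 | 5.0% |
| 0.1, median split | 0.33 | 0.1 × 0.33 = 0.033 | 5.3% |
| 0.1, middle 20% ungrouped | 0.40 | 0.1 × 0.40 = 0.040 | 5.5% |
| 0.2, median split | 0.68 | 0.2 × 0.68 = 0.135 | 10.8% |
| 0.2, middle 20% ungrouped | 0.78 | 0.2 × 0.78 = 0.157 | 12.9% |

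With the overall SD, the last row becomes 13.6%. If either drift is zero, the expected spurious difference is zero and the rate stays at 5%.

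**Step 5, endpoint 2.** Pre-operative values that are only looked up were fixed before the clock started, so time since surgery cannot alter them. For those values it can only blur who falls in which group. Pupil, iDesign and remeasured values are taken at the variable time and could be affected directly. The documents give no basis for a magnitude.

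**The case against.** The strongest reply is that no section shows acuity or satisfaction changing between 1 and 6 months, that a window of this kind is an ordinary choice in an observational study, and that without drift there is neither bias nor noise to remove. This stands: the whole effect is conditional. Confounding also needs drift in both DCIVA and satisfaction; a reader might think that one is enough, but step 4 shows that it is not.

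A reader might also suppose a one-month gap between groups. With satisfaction drift of 0.1 to 0.2 SD per month, that gives spurious differences of 0.1 to 0.2 SD and false-positive rates of about 8% to 18%. The arithmetic is right but the premise is not supported. One month is 1/0.275 = 3.6 standard errors of chance imbalance, and on a median split it needs DCIVA to drift by about 0.3 SD per month, more than is being assumed for satisfaction.

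Nor do the documents support reading the biometry results as confounded throughout. The stated aim is pre-operative recognition, and values recorded before surgery are immune.

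Finally, the eligibility list might be read as admitting patients at any time after surgery. A patient seen at one year would meet every listed criterion, but would fall outside the window in the design section. The list and the invitation are silent on timing; they do not contradict the window. This is a drafting omission.

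What the reply leaves standing is that time since surgery is unbalanced by design, appears in no comparison, and has to be known anyway if the window is to be applied.

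**Conclusion.** The point holds as a minor, conditional weakness. Endpoint 3 can be confounded by time since surgery if DCIVA and satisfaction both change over months 1 to 6. At an assumed drift of 0.1 to 0.2 SD per month in both, evenly spread visits and 55 per group, the false-positive rate is about 5% to 13% instead of 5%. At 0.05 SD per month it is indistinguishable from 5%. The loss of precision is a few points of power at most over the same drift range. For endpoint 2 the concern covers visit-measured values and blurring of the grouping only. The documents do not establish that any drift exists, so this is a reason for an inexpensive safeguard and not evidence that the results will be biased.

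**What to change.** 1. Record the surgery date for each eye and derive months since second-eye surgery at the visit. Report its distribution by group.
2. Prespecify months since second-eye surgery as a covariate in the endpoint 3 comparison and, for values measured at the visit (pupil, iDesign, remeasured biometry), in the endpoint 2 regression. Note for each biometric value whether it was looked up or remeasured, so that this can be applied.
3. As an editorial step, reconcile the eligibility list with the 1–6-month window in Overall Study Design, and state which eye's surgery starts the window.

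**Cost.** One degree of freedom per model and one derived variable. Surgery dates are not among the listed data items, but the window cannot be applied without them. Under the plan's own rule a seventh variable gives 50 + 8 × 7 = 106 read as a total, still within 110. Read per arm it gives 2 × 106 = 212, but on that reading 110 already falls short of the 196 needed for six variables. A few late patients may not qualify once the eligibility list and the window agree.

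### All three primary endpoints compare two groups cut from binocular DCIVA, which loses power against the DCIVA score itself, and near acuity enters no group definition or endpoint

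*Combined protocol and SAP*

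**What the plan says.** Under Study Objectives, the aim is to find preoperative measurements that "could indicate increased intermediate or near vision in a patient receiving an Eyhance IOL".

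Overall Study Design forms two groups from binocular photopic acuity corrected to plano. The minimal-intermediate "group is defined by BCDVA of 0.1 logMAR or better but a DCIVA of 0.4 logMAR or worse". The enhanced intermediate/near group "is defined by BCDVA of 0.1 logMAR or better and a DCIVA of 0.3 logMAR or better", with DCIVA taken at 66 cm. The section continues: "The two groups will be compared to assess which patient biometric properties" raise near or intermediate vision.

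All three Primary Clinical Endpoints use these groups. The first compares the groups. The second is "To determine if any statistically significant differences in biometric data exists between the two groups"; it calls for multiple regression but names no dependent variable. The third is "Comparison of a patient satisfaction survey between the two groups".

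Two other places matter. The Exclusions list "Postoperative CDVA worse than 0.10 logMAR", so the BCDVA part of both definitions largely repeats an entry limit. The Visit Schedule includes "Binocular distance corrected near visually acuity", so near acuity is collected, monocularly as well.

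**The concern.** BCDVA of 0.1 or better is in both definitions, so DCIVA alone decides membership. Three consequences follow.

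- **Lost information.** DCIVA is a graded score. Once it is cut, a patient at 0.10 counts the same as one at 0.30. For a fixed number of patients and a roughly linear relation, a true predictor is harder to detect, and more so as the groups become unequal. The documents give no expected split.
- **Unassigned patients.** Scores strictly between 0.3 and 0.4 fit neither definition, and no handling rule is given. They occur with letter scoring but not with whole-line scoring; the scoring method is not stated.
- **Near vision.** It is in the objective and in one group's label, but the definition uses 66 cm only. A predictor of near vision could be seen only indirectly, through its link with 66 cm acuity.

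Finding predictors is the purpose of the study, so a weaker test bears directly on whether it can answer its question.

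**Working it through.** **Inputs from the documents.** About 110 patients, six predictors, alpha 0.05 and 80% power (Number of Subjects); cuts at 0.3 and 0.4 logMAR (Overall Study Design). The sample size rule gives 50 + 8 × 6 = 98, or 196 if its per-arm wording is applied to two arms. Neither is 110. That is a separate matter; 110 is used here as stated.

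**Assumptions, because the documents give no figures.** DCIVA normal with mean 0.20, 0.25, 0.30 or 0.35 and SD 0.10 or 0.15; letter scoring (steps of 0.02) or whole-line scoring (steps of 0.1); six independent predictors, one correlated r = 0.30 with DCIVA; two-sided testing. This makes 4 × 2 × 2 = 16 settings.

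**Efficiency by formula, letter scoring.** With steps of 0.02, a score of 0.30 or better corresponds to an underlying value below 0.31, and 0.40 or worse to one above 0.39. Let a = (0.31 − mean)/SD, b = (0.39 − mean)/SD, p₁ = Φ(a), p₀ = 1 − Φ(b), m₁ = −φ(a)/p₁ and m₀ = φ(b)/p₀. Relative to continuous DCIVA, the efficiency per measured patient is

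(m₀ − m₁)² × p₁p₀/(p₁ + p₀).

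- Mean 0.35, SD 0.10: p₁ = p₀ = 0.345 and m₀ − m₁ = 2.14, giving 4.57 × 0.172 = 0.79.
- Mean 0.20, SD 0.10: p₁ = 0.864, p₀ = 0.029 and m₀ − m₁ = 2.54, giving 6.44 × 0.0278 = 0.18.

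Whole-line scoring amounts to a single cut at 0.35. Its efficiency is at most 0.64, reached with a 50:50 split.

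**Simulated power** (2,000 studies per setting, N = 110, r = 0.30, six-predictor logistic model with Wald test):

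| Mean | SD | Expected minimal group (letter) | Expected in neither group (letter) | Logistic, letter | Logistic, whole-line |
|---|---|---|---|---|---|
| 0.20 | 0.10 | 3 | 12 | 0.12 | 0.33 |
| 0.25 | 0.10 | 9 | 21 | 0.45 | 0.54 |
| 0.30 | 0.10 | 20 | 30 | 0.71 | 0.67 |
| 0.35 | 0.10 | 38 | 34 | 0.79 | 0.71 |
| 0.20 | 0.15 | 11 | 14 | 0.49 | 0.53 |
| 0.25 | 0.15 | 19 | 19 | 0.64 | 0.61 |
| 0.30 | 0.15 | 30 | 22 | 0.74 | 0.69 |
| 0.35 | 0.15 | 43 | 23 | 0.78 | 0.71 |

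Linear regression on continuous DCIVA gives 0.85-0.89 in all 16 settings. The 0.12 should be discounted: about three patients are in the minimal group and 22% of fits failed (under 1% elsewhere). The other 15 settings give 0.33-0.79. Under letter scoring, 12 to 34 of 110 patients (11-31%) are in neither group.

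**Does the loss depend on the test?** No. A likelihood-ratio test gives 0.24-0.82 and a two-sample t-test of the predictor 0.25-0.80.

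**Does it depend on r?** The direction does not:

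| r | Two-group t-test | Linear regression |
|---|---|---|
| 0.20 | 0.13-0.47 | 0.48-0.57 |
| 0.30 | 0.25-0.80 | 0.84-0.90 |
| 0.40 | 0.38-0.97 | 0.98-0.99 |

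**Near vision.** This part needs no arithmetic. Setting the objective, the visit tests, the group definitions and the endpoints side by side, near acuity is in the first two and absent from the last two.

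**The case against.** The strongest reply has four parts.

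1. *The plan names no dependent variable.* It calls for multiple regression and is sized by a regression rule, so continuous DCIVA is not ruled out. This is true. But the regression sentence serves an endpoint worded as differences between the two groups, and nothing mentions the score as an outcome. If continuous DCIVA is intended, saying so is most of the fix.

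2. *The loss comes from imbalance and unassigned patients at a fixed 110, not from grouping as such.* In a check with r = 0.30, letter scoring and a t-test, filling 55 patients per group gave 0.88-0.99. Enrolling until 110 were classified gave 0.85-0.94 at means 0.30-0.35, but only 0.27-0.74 at means 0.20-0.25. This stands as a condition. However, the plan states no quota, and these designs measure more patients. At SD 0.10, filling the minimal group takes about 55/0.345 ≈ 160 patients at mean 0.35 and about 55/0.029 ≈ 1,900 at mean 0.20.

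3. *The size is assumed, and a linear normal model favours the continuous analysis.* The hypothesis speaks of some patients doing vastly better, which suits a responder definition. It is right that only the direction is firm. In the balanced letter-scored case the loss is only about 0.1. Keeping the groups as description preserves the responder view.

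4. *The remedy brings in a multiplicity correction.* Holm across 12 tests is open to debate and lowers power below 80% at r = 0.30. The core change does not depend on that choice.

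**Conclusion.** The concern holds. That all three endpoints rest on groups separated only by DCIVA at 66 cm, and that near acuity is in no group definition or endpoint, follows from the text alone. That grouping loses power is firm for a fixed number of measured patients and a roughly linear relation. With 110 patients and r = 0.30, the two-group logistic model stays below 80% power in all 16 assumed settings, while the continuous analysis exceeds it in all 16. How much is lost, from about 0.1 to well over half of the power, depends on a DCIVA distribution that the documents do not give. The unassigned patients arise only with letter scoring, but whole-line scoring, which leaves none, still gives only 0.33-0.71. The study can proceed; the analysis should be changed before the data are analysed.

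**What to change.** - Make the primary analysis a linear regression of continuous binocular photopic DCIVA on the six listed biometric variables, in all enrolled patients.
- Fit the same model to binocular DCNVA, so that near vision has its own named outcome.
- Control multiplicity with Holm across the 6 × 2 = 12 predictor-by-outcome tests at two-sided 0.05.
- Relate satisfaction to continuous DCIVA.
- Keep the two groups as a descriptive table. State how acuity is scored and where scores between 0.3 and 0.4 are shown.
- Adjust for BCDVA only as a sensitivity analysis: it is a postoperative outcome from the same visit, which pupil size or spherical aberration may affect.

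**Cost.** The wording of the primary analysis changes; no visit, test or patient is added. Results are expressed per 0.1 logMAR rather than as two labelled groups. Testing at 0.05/12 lowers power at r = 0.30 to 0.55-0.61 by simulation; a noncentral t calculation gives 0.61 at r = 0.30 and 0.81 at r = 0.35, so 80% needs r of about 0.35. These are Bonferroni figures, and Holm does no worse. The two-group logistic model corrected for only six tests (0.05/6) has 0.01-0.50, lower than the continuous analysis in all 16 settings.

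### The arms are separated only by absolute DCIVA under a shared BCDVA limit, so the enhanced arm is likely also to see better at distance, and endpoints 2 and 3 as written do not allow for this

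*Combined protocol and SAP*

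**What the plan says.** Under Overall Study Design, patients are grouped "based on mean photopic binocular BCDVA and DCIVA (at 66 cm) of patients with bilateral Eyhance IOLs corrected to plano sphere". The minimal arm "is defined by BCDVA of 0.1 logMAR or better but a DCIVA of 0.4 logMAR or worse". The enhanced arm "is defined by BCDVA of 0.1 logMAR or better and a DCIVA of 0.3 logMAR or better". The 0.1 figure is also the eligibility limit: exclusion 10 removes patients with "Postoperative CDVA worse than 0.10 logMAR (20/25 snellen"), and the selection criteria apply to each study eye.

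The Visit Schedule lists "Binocular best corrected distance visual acuity" as item 5, so the measure exists for every subject. It is not among the regression variables under Number of Subjects, which are all biometric: "Assuming 6 variables (pupil size, q value, spherical aberration, AC depth, axial length, average K power").

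Under Primary Clinical Endpoints, item 2 calls for multiple regression on biometric data. Item 3 compares a satisfaction survey between the arms "to determine if the enhanced vision plays a statistically significant difference in" perceived quality of vision or life. Neither item mentions adjustment for distance acuity. Item 1 names mean binocular BCDVA and DCIVA as the basis of the grouping.

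**The concern.** A shared upper limit caps BCDVA but does not equalise it. There is no lower bound, no matching, and no measure of the drop from distance to 66 cm. A patient can therefore reach the enhanced arm either by losing little between distance and 66 cm or by starting from very sharp distance vision.

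Two readings of the results are at stake. In endpoint 3, a satisfaction difference that comes from better distance vision could be credited to enhanced intermediate vision. In endpoint 2, a biometric variable tied to general sharpness and one tied to intermediate range would look alike, and the plan has no analysis that tells them apart.

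**Working it through.** **The plan's own figure.** The sample-size rule with m = 6 gives 50 + 8 × 6 = 98 per arm, or 196 for two arms. The printed total is about 110 patients, so it is not reproduced. That is a separate matter. This point does not depend on N, and 110 is used below only because it is the stated number.

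**Arm definitions.** Write DCIVA = BCDVA + drop, which is an identity. A patient is enhanced if drop ≤ 0.30 − BCDVA, and minimal if drop ≥ 0.40 − BCDVA.

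| BCDVA | Enhanced if drop is | Minimal if drop is |
|---|---|---|
| -0.10 | ≤ 0.40 | ≥ 0.50 |
| 0.10 | ≤ 0.20 | ≥ 0.30 |

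- Same drop, opposite arms: with a drop of 0.35, BCDVA -0.10 gives DCIVA 0.25 (enhanced) and BCDVA 0.10 gives 0.45 (minimal).
- Order reversed: BCDVA -0.10 with drop 0.40 gives DCIVA 0.30 (enhanced), while BCDVA 0.10 with drop 0.30 gives DCIVA 0.40 (minimal). The patient who loses less is in the minimal arm.

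**Likely distance gap between arms.** The documents give no SDs and no correlation, so these inputs are assumed: BCDVA mean 0.00, SD 0.07, cut at 0.10; drop SD 0.10, mean 0.30 to 0.35. Before the cut at 0.10, Cov(BCDVA, DCIVA) = SD_B² + ρ × SD_B × SD_drop. This is zero at ρ = −SD_B/SD_drop = −0.07/0.10 = −0.7. Simulation with the printed cut-offs agrees:

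| Correlation of BCDVA with drop | Enhanced arm better at distance by |
|---|---|
| 0 | about 0.07 logMAR |
| -0.3 | about 0.05 |
| -0.5 | about 0.03 |
| -0.7 | about 0 |

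Over a wider grid (BCDVA mean -0.02, SD 0.05 or 0.08; drop mean 0.25 or 0.35, SD 0.08 or 0.12), the gap is 0.04 to 0.12 at correlations of 0 or +0.3. At -0.6 it runs from -0.03 to +0.07, where a negative value means the enhanced arm is worse at distance.

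**Endpoint 3.** Suppose satisfaction depends on BCDVA alone, and BCDVA and drop are independent with SDs 0.07 and 0.10. One simulation found a significant difference between arms in 28% to 34% of studies unadjusted. A repeat, with satisfaction correlated 0.3 with BCDVA before the cut, gave 18% to 24% when 110 are enrolled and patients between 0.3 and 0.4 drop out, and 31% to 36% with 55 analysed per arm. The unadjusted rate therefore depends on the assumed link and the number analysed. With BCDVA as a covariate the rate was 4% to 6% throughout, including at the negative correlations tried.

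**Endpoint 2.** Take a marker correlated 0.3 with BCDVA and unrelated to the drop, with BCDVA and drop independent and 110 enrolled. It is significant between arms in 14% to 30% of studies over the SDs tried (BCDVA 0.05 to 0.09, drop 0.08 to 0.12), against 4% to 5% with BCDVA in the model.

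That result for covariate adjustment needs independence. If BCDVA and drop are correlated -0.5, the marker's partial correlation with the drop given BCDVA is (0 + 0.3 × 0.5)/√[(1 − 0.09)(1 − 0.25)] = 0.15/0.826 = 0.18, although its plain correlation is zero. In simulation the BCDVA-adjusted arm model then rejects in 28% to 36% of studies, against 6% to 7% when DCIVA minus BCDVA is the outcome. The two methods are not interchangeable.

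**The case against.** The strongest reply is that the study asks about attained vision. Study Objectives and endpoint 2 seek pre-operative findings that point to better intermediate or near vision, and no section defines the outcome as a drop from distance. A variable that predicts DCIVA through general sharpness is a true predictor of that outcome, so the 14% to 30% above is not a false-positive rate for the plan's question. BCDVA is also measured after surgery, so conditioning on it does not suit pre-operative recognition. This stands. A reader might infer that a variable should count only if it survives adjustment for BCDVA; the documents do not support that rule.

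Two other strong readings also fail. A reader might infer that the enhanced arm is bound to see better at distance. That depends on a correlation the documents do not give, and under a strong enough negative one the gap vanishes or reverses. A reader might also infer that the study cannot separate range from sharpness. That is true of the analysis as written but not of the data, because binocular BCDVA is collected in everyone. Endpoint 1 might also bring an imbalance to light, though seeing it does not adjust endpoints 2 or 3.

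The reply does not reach endpoint 3, whose wording credits a satisfaction difference to the enhanced vision while the arms may also differ at distance.

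**Conclusion.** The point holds in a limited form. It is certain from the definitions that the split can mix intermediate range with sharpness and can order patients against their drop. It is likely, but not certain, that the enhanced arm sees better at distance: about 0.07 logMAR under independence with SDs of 0.07 and 0.10, and about zero at a correlation of -0.7. All sizes rest on assumed SDs and correlations.

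The consequence is firmest for endpoint 3, where a difference caused by distance acuity alone could be misattributed in roughly one study in five to one in three under independence. For endpoint 2 the main analysis answers the stated objective and should stay. What is missing is a supplementary analysis showing how a predictor acts.

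**What to change.** - **Endpoint 3:** add binocular BCDVA as a covariate in the comparison of satisfaction between arms, so that a difference due to distance acuity is not credited to enhanced intermediate vision.
- **Endpoint 2:** keep the comparison of the attained-DCIVA arms as the main result. Add one pre-specified supplementary regression of binocular DCIVA minus binocular BCDVA on the same biometric variables. It needs no arms, so it can also use patients whose DCIVA lies between 0.3 and 0.4. Present it as showing whether a predictor acts on intermediate range or on overall sharpness, not as a test a predictor must pass.
- **Reporting:** give mean binocular BCDVA by arm.
- **Wording:** do not describe covariate adjustment and the difference score as equivalent.

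The cost is a little extra analysis and one degree of freedom in endpoint 3. No visit, measurement or eligibility rule changes, because binocular BCDVA is already collected.
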